3.1.6 Physician Data Collection

A Web-based electronic data capture (EDC) system will be used in this study. An invitation will be sent to the selected sample of physicians, inviting them to participate and providing a link to the Web-based questionnaire. During the data collection period, invitations will be made via e-mail or issued by phone to each sampled physician up to two times. Each invited physician will be asked to log in to the study Web site by entering a unique identification number and password assigned to each participant and provided in the invitation to participate. The questionnaire will begin with informed consent. After participants consent, they will be prompted to complete the questionnaire. A screening question will be included at the beginning of the questionnaire to confirm that the physician has prescribed

rivaroxaban at least once within the past 6 months for at least one of the two new indications.

The questionnaire will be self-administered (closed-ended questions with predefined answers) and can be completed at the participants' convenience. Although participants will be encouraged to complete the questionnaire in a timely manner, once they start the questionnaire, they will be able to stop at any point and, at a later time, pick up where they left off, should that be necessary. Participants will not be able to go back and change answers to previous questions. This restriction minimizes the likelihood of the respondent searching for answers via the Web or other sources.

Participants will also not be allowed to access the questionnaire once it has been completed. Based on potential country-specific requirements, the recruitment process and physician questionnaire may be different between countries. Country-specific differences will be described and appended to the final study protocol.

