3.1.4 Physician Sample Size

The study will target 300 participating physicians per country, for a total of approximately 1,500 physicians overall¹, to allow reasonable precision around estimates of physicians' knowledge and understanding of the prescriber guide. For example, if we assume that the total sample of participating physicians can be treated as a simple random sample and that the percent of correct responses to a true/false question is 85%, then for a sample of size 300, the two-sided 95% confidence interval will be 80.4% to 88.8%. Table 1 shows the exact 95% confidence limits assuming various combinations of sample size and correct response percentages.

Table 1. Exact 95% Confidence Limits for Various Combinations of Sample Size and Correct Response Percentage

| Sample Size | Correct Response (%) | Lower 95% Confidence Limit (%) | Upper 95% Confidence Limit (%) |
|-------------|----------------------|--------------------------------|--------------------------------|
| 100 | 80 | 70.8 | 87.3 |
| 100 | 85 | 76.5 | 91.4 |
| 300 | 80 | 75.0 | 84.4 |
| 300 | 85 | 80.4 | 88.8 |
| 500 | 80 | 76.2 | 83.4 |
| 500 | 85 | 81.6 | 88.0 |
| 1,500 | 80 | 77.9 | 82.0 |
| 1,500 | 85 | 83.1 | 86.8 |

¹ Due to drug approval delays in Italy, the 18-month assessment will not include Italy. Therefore, the total sample size for the 18-month assessment will be 1,200 physicians.

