3.1.5 Physician Questionnaire Development

Standard survey methodologic principles have been used to develop the physician questionnaire, which will assess physicians' knowledge of the following concepts as outlined in the prescriber guide and educational materials:

- Switching from or to rivaroxaban treatment
- Necessity of taking the 15-mg and 20-mg tablets with food
- Use of coagulation tests and their interpretation
- Dosing recommendations
- Perioperative management
- Populations at higher risk of bleeding
- Necessity of providing all patients with a patient alert card and counselling about the details of the patient alert card

Physicians will be asked about their receipt and use of the prescriber guide (Appendix A) as well as counselling of patients and distribution of the patient alert card. In addition, physicians will be asked to characterise their practice in terms of years in practice, size of practice, and history of treating patients with the diagnoses of interest. Other characteristics will be collected to facilitate stratified analyses to explore factors associated with knowledge and behaviour. The physician questionnaire is designed to take 10-15 minutes to complete. The physician questionnaire has been cognitively tested with physicians in each of the target countries. Section 3.3 provides a detailed description of the cognitive pretesting process. Modifications have been made to the questionnaire based on the pretesting results and additional feedback from the sponsor. The final version of the questionnaire can be found in Appendix C. Some modifications to the questionnaire are anticipated based on country-specific requirements.

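### The no-going-back rule in the physician Web survey protects only submitted answers; look-up of the question on screen is uncontrolled and may inflate measured knowledge by an unknown amount

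*Protocol*

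**What the plan says.** Protocol Section 3.1.6 describes an unsupervised, self-administered Web questionnaire that "can be completed at the participants' convenience". Physicians are encouraged to finish promptly, but once they have started, "they will be able to stop at any point and, at a later time, pick up where they left off". No maximum gap, session limit or time limit is stated, and the knowledge items are not treated differently from the rest.

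The next two sentences set out the control and its purpose: "Participants will not be able to go back and change answers to previous questions", and "This restriction minimizes the likelihood of the respondent searching for answers via the Web or other sources". The section adds a further closure at the end: "Participants will also not be allowed to access the questionnaire once it has been completed".

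In Appendix C the knowledge items are Q5 to Q18, and a link to the Prescriber Guide appears only after the closing text. Nothing in Appendix C asks the physician to answer from memory. Patients are handled differently. Section 3.2.6 and the Appendix D instructions tell them to complete the first questionnaire without consulting the alert card, and Appendix D extends this to other educational materials on the drug. Section 5 lists patients changing answers on paper, and sites educating patients more than usual, as limitations. It does not mention physicians looking up answers.

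**The concern.** The rationale does not follow from the restriction. Blocking backward navigation governs questions already answered, whereas look-up concerns the question still on screen. A physician unsure of an item can leave the survey there, consult the guide or the Web, and resume at the same item with nothing yet submitted. The resume rule makes this easier, in the same paragraph that claims to limit searching.

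Section 2 sets out to assess physicians' knowledge and understanding of the key safety information, not their ability to find it. Section 5 says the assessment takes place after physicians have received the prescriber guide, so the source of the answers is expected to be within reach. Any look-up would push the percentage correct upwards, and the confidence limits in Table 1 would not reflect it because they describe sampling error alone.

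This cannot all be left to a later analysis plan. Section 3.1.6 fixes how the data capture system behaves. If session breaks and item times are not recorded while the survey is in the field, no later analysis can recover them.

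**Working it through.** **Step 1: which kinds of look-up the stated controls reach.**

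| Behaviour | Control in Section 3.1.6 or Appendix C | Covered? |
|---|---|---|
| Changing a submitted answer after a later look-up | No return to previous questions | Yes |
| Changing a submitted answer after a cue in a later item (the INR options in Q11 and Q12 bear on Q10) | No return to previous questions | Yes |
| Revising after opening the guide link at the end | Closed on completion; link comes after the last question | Yes |
| Pausing at an unanswered item, looking it up, resuming | None; resume is allowed at any point | No |
| Looking up an unanswered item without pausing (second window, printed guide) | None; no instruction in Appendix C | No |

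**Step 2: the protocol's own precision.** Section 3.1.4 states: "The study will target 300 participating physicians per country, for a total of approximately 1,500 physicians overall". Its example is 85% correct. Exact (Clopper-Pearson) limits with x correct out of n are

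- lower = Beta quantile at 0.025 with parameters x and n − x + 1
- upper = Beta quantile at 0.975 with parameters x + 1 and n − x

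For n = 300, x = 255, this gives 80.4% to 88.8%, as stated, with half-width (88.8 − 80.4)/2 = 4.2 points. For n = 1,500, x = 1,275, it gives 83.1% to 86.8%, as in Table 1, with half-width (86.8 − 83.1)/2 = 1.85, or about 1.9 points. All eight rows of Table 1 reproduce to one decimal, so the table is correct for sampling error.

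**Step 3: how look-up would shift an observed 85%.** Let k be the proportion who would answer correctly unaided. Let f be the share of the others who look up the item, by pausing or not, and then answer it correctly. Unaided correct answers are assumed unaffected. Then

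observed = k + (1 − k)f, so k = (observed − f)/(1 − f).

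The documents give no value for f. The range of 5% to 30% is an assumption.

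| Assumed f | Unaided knowledge k when 85% is observed | Upward shift (points) |
|---|---|---|
| 0% | 85.0% | 0 |
| 5% | (0.85 − 0.05)/0.95 = 84.2% | 0.8 |
| 10% | (0.85 − 0.10)/0.90 = 83.3% | 1.7 |
| 20% | (0.85 − 0.20)/0.80 = 81.25% | 3.75 |
| 30% | (0.85 − 0.30)/0.70 = 78.6% | 6.4 |

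**Step 4: when the shift would exceed the half-width.** The shift is 0.85 − k = 0.15f/(1 − f). Setting this equal to a half-width h gives f = h/(0.15 + h).

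- n = 1,500: 0.0185/0.1685 = 0.11, so above about 11%.
- n = 300: 0.042/0.192 = 0.22, so above about 22%.

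The shift does not shrink as the sample grows, so it weighs more on the pooled estimate than on a single country's.

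**The case against.** The protocol claims only to reduce the likelihood of searching, not to prevent it, and the restriction does real work: it stops correction after later cues or a later look-up. Closing the survey on completion and placing the guide link last support it. A reader might infer from the gap that the stated protection does not exist at all. The first three rows of the first table show otherwise.

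A reader might also infer that physician knowledge will be overstated. The documents do not show that. They give no look-up rate, and there are reasons for it to be low: Section 3.5.3 says the questionnaires collect no identifying information, Section 3.5.4 says the sponsor receives aggregate data only, and every item from Q5 to Q18 offers a don't-know option.

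Third, pausing is not what makes look-up possible. In an unsupervised Web survey a physician can consult a source without leaving the session, so forcing a single session would not close the route. It could also raise break-offs, in a study whose Section 5 already names non-response as a limitation. Letting busy prescribers resume is a defensible choice.

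Finally, Section 4 leaves detailed methods to an analysis plan that is not at hand, so the absence of an analysis by interruption is not itself a fault.

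All of this stands. It limits the claim, but it does not repair the rationale sentence, supply the missing instruction, or secure the timing data that such an analysis would need.

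**Conclusion.** The point holds in a limited form. The restriction in Section 3.1.6 gives partial protection, covering submitted answers only. Stop-and-resume works against its stated purpose, and physicians, unlike patients, are not asked to answer unaided. Look-up of the current item is therefore uncontrolled.

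Any resulting bias would most likely be upward. Whether it occurs, and how large it is, cannot be determined from the protocol. The range of 0.8 to 6.4 points at an observed 85% rests entirely on the assumed 5% to 30% of non-knowers and on every such look-up succeeding. It includes look-up without a pause, so it is not the effect of the resume function alone. With no look-up there is no bias. The illustration shows only that a moderate rate would be enough to matter against the precision the protocol plans for.

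**What to change.** Keep stop-and-resume, and make four changes before fielding:

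1. Have the data capture system record session breaks and time per item for Q5 to Q18.
2. Repeat the main knowledge tables excluding respondents with a break or an unusually long item time within Q5 to Q18, with the cut-off for unusually long set before the data are seen.
3. Add to Appendix C the instruction already given to patients, to answer without consulting materials.
4. Reword the rationale in Section 3.1.6 so that it claims only protection of submitted answers, and list physician look-up as a limitation in Section 5.

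The cost is a data-capture setting, one extra table and some wording. The exclusion will also drop physicians interrupted for ordinary reasons and will miss quick look-ups, so it is a sensitivity analysis and should not replace the main tables. If the two sets agree, that is some reassurance; if they differ, the report should show both.

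Requiring Q5 to Q18 in one session is optional. It is feasible, given that "The physician questionnaire is designed to take 10-15 minutes to complete", but it may increase break-offs and does not stop look-up within the session.

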3.2 Patient Assessment

3.2.1 Patient Assessment Overview

Patients taking rivaroxaban will be identified through a diverse selection of medical practices representing specialties that prescribe rivaroxaban across the target countries. The medical practices selected for participation in the patient assessment will not be included in the physician assessment described above; however, they will be asked to complete the physician questionnaire to allow exploratory evaluation of the possible impact of the study on physician knowledge and to evaluate patient responses by level of knowledge of their physician. Patients will be invited to participate by their physicians and will complete a paper questionnaire. Data will be analysed using descriptive tables summarising demographics, results, and other available characteristics. Timing and sequence of study initiation in each country will be determined based upon the product launch schedule and timing of ethics approval.

3.2.2 Patient Population and Eligibility

Patients will be identified through selection of a diverse set of medical practices across the five targeted countries. To be eligible for the study, the patients must meet all of the following criteria:

- Patient has taken rivaroxaban within the last 3 months for prevention of stroke and systemic embolism in adult patients with non-valvular atrial fibrillation (SPAF) or

treatment of DVT and prevention of recurrent DVT and pulmonary embolism (PE) following an acute DVT in adults.

- Patient is aged 18 years or older.
- Patient is able to understand and complete the consent form and patient questionnaire.
- Patient can read and understand the native language of the country in which the study is being conducted.
- Patient has not participated in a clinical trial for a treatment to prevent blood clots in the past 12 months.

3.2.3 Patient Selection and Recruitment

The study will target 100 patients per country to complete the assessment. This estimate is based upon the anticipated number of eligible patients for participation. This target study size is dependent upon the actual number of patients filling a prescription within the established time frame and on response rates for the study. At least 10 physician practices in each country will be selected from a list of eligible physicians in order to identify and recruit a sufficient number of eligible patients (up to 10 patients per physician). Several factors will be evaluated to ensure a diverse representation of sites, including geographic location, physician specialty, and patient mix. To participate in the study, sites must (1) see a sufficient number of eligible patients; (2) be able to provide a semiprivate space for patient recruitment, the consent process, and completion of the patient-reported questionnaire; and (3) have a staff member available to coordinate research activities.

Physicians who are selected to participate in the patient assessment will be excluded from participating in the physician assessment.

Participating physicians will also be asked to collect a limited amount of de-identified information on all patients receiving rivaroxaban so that characteristics of participants can be compared with non-participants.

Patients will be eligible if they have taken rivaroxaban within the last 3 months for either SPAF or DVT treatment and secondary prevention. The patient sampling methodology will be designed with the goal of maximising the probability that each patient treated with rivaroxaban will have an equal opportunity to be selected. In some sites, it is likely that all treated patients will be selected. The sampling approach for those sites with larger numbers of patients will be customised for the site (based on patient volume) and will be devised to achieve an efficient method of obtaining a representative patient sample in centres with varying patient administration systems. The sites will be asked to recruit the patients for the

study when the patient is at the physician practice for a previously scheduled visit, or by telephone.

3.2.4 Patient Sample Size

The study will target 100 patients per country, for a total 500 patients overall¹, to allow reasonable precision around estimates of patients' knowledge and understanding of the patient alert card at the study level. Since we plan to recruit up to 10 patients per physician practice, the responses from patients within the same practice may be correlated. Assuming no intraclass correlation and the percentage of correct responses to a true/false question is 50.0%, then for a sample of size 500, the two-sided 95% confidence interval will be 45.6% to 54.4%; whereas the corresponding confidence interval will be 41.2% to 58.8% if there is an intraclass correlation of 0.33. Table 2 shows 95% confidence limits assuming various combinations of sample size, correct response percentages, and intra-class correlation coefficients.

Table 2. Confidence Limits (95%) for Various Combinations of Sample Size, Correct Response Percentage, and Intraclass Correlation Coefficient

| Patient Sample Size | Intraclass Correlation Coefficient ^a | Correct Response (%) | Lower 95% Confidence Limit (%) | Upper 95% Confidence Limit (%) |
|---------------------|---|----------------------|--------------------------------|--------------------------------|
| 100 | 0.00 | 50 | 40.2 | 59.8 |
| 100 | 0.11 | 50 | 36.1 | 63.9 |
| 100 | 0.33 | 50 | 30.4 | 69.6 |
| 100 | 0.00 | 80 | 72.2 | 87.8 |
| 100 | 0.11 | 80 | 68.9 | 91.1 |
| 100 | 0.33 | 80 | 64.3 | 95.7 |
| 200 | 0.00 | 50 | 43.1 | 56.9 |
| 200 | 0.11 | 50 | 40.2 | 59.8 |
| 200 | 0.33 | 50 | 36.1 | 63.9 |
| 200 | 0.00 | 80 | 74.5 | 85.5 |
| 200 | 0.11 | 80 | 72.2 | 87.8 |
| 200 | 0.33 | 80 | 68.9 | 91.1 |
| 500 | 0.00 | 50 | 45.6 | 54.4 |
| 500 | 0.11 | 50 | 43.8 | 56.2 |
| 500 | 0.33 | 50 | 41.2 | 58.8 |

¹ Due to drug approval delays in Italy, the 18-month assessment will not include Italy. Therefore, the total sample size for the 18-month assessment will be 400 patients.

| Patient Sample Size | Intraclass Correlation Coefficient^a | Correct Response (%) | Lower 95% Confidence Limit (%) | Upper 95% Confidence Limit (%) |
|----------------------------|---|-----------------------------|---------------------------------------|---------------------------------------|
| 500 | 0.00 | 80 | 76.5 | 83.5 |
| 500 | 0.11 | 80 | 75.0 | 85.0 |
| 500 | 0.33 | 80 | 73.0 | 87.0 |

Note: Table calculations assume that, on average, 10 patients come from each practice (cluster).

^a With an average cluster size of 10 patients, correlation coefficients of 0.11 and 0.33 correspond with a design effect of 2 and 4, respectively.

3.2.5 Patient Questionnaire Development

The patient questionnaire has also been developed following standard survey methodologic principles and has been cognitively tested with patients in each of the target countries. Modifications have been made to the questionnaire based on the results of testing and additional feedback from the sponsor. The final version of the questionnaire can be found in Appendix D. Some modifications to the questionnaire are anticipated based on country-specific requirements. The questionnaire will assess patient knowledge of the following concepts:

- Receipt and use of the patient alert card
- Knowledge of the key safety messages outlined in the patient alert card:
 - Signs or symptoms of bleeding and when to seek attention from a health care provider
 - Importance of treatment compliance
 - Necessity of taking the 15-mg and 20-mg tablets with food
 - Necessity of carrying the patient alert card at all times
 - Necessity of informing HCPs that they are taking rivaroxaban if they need to have surgery or invasive procedures

The questionnaire includes demographics and other patient information to help characterise patterns of knowledge and behaviour through stratification of results. The questionnaire has been designed to take approximately 20 minutes to complete.

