2 SPECIFIC AIMS

The primary objective of this cross-sectional epidemiologic study is to measure physician and patient awareness and understanding of the key messages in the prescriber guide and patient alert card.

Specifically, the following objectives will be addressed:

- Investigate whether physicians and their patients have received the educational materials.
- Assess knowledge and understanding among physicians regarding key safety information contained in the prescriber guide and assess how physicians use the materials in their daily practice.
- Assess knowledge and understanding of patients regarding the key safety information contained in the patient alert card and determine if the patients use and carry the patient alert card with them.

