Appendix B.
Xarelto Patient Alert Card

What should I know about Xarelto®?

- Xarelto® thins the blood, which prevents you from dangerous blood clots.
- Xarelto® must be taken exactly as prescribed by your doctor. To ensure optimal protection from blood clots, **never skip a dose.**
- You must not stop taking Xarelto® without first talking to your doctor as your risk of blood clots may increase.
- Speak to your health care provider prior to any intake of other medication.
- Inform your health care providers about Xarelto® intake prior to any surgery or invasive procedure.

When should I seek advice from my health care provider?

When taking a blood thinner such as Xarelto® it is important to be aware of its possible side effects. Bleeding is the most common side effect. Do not start taking Xarelto® if you are at risk of abnormal bleeding, without first discussing this with your doctor.

Tell your health care provider right away if you have any signs or symptoms of bleeding such as the following:

- pain
- swelling or discomfort
- headache, dizziness or weakness
- unusual bruising, nosebleeds, bleeding of gums, bleeding from cuts that take a long time to stop

- menstrual flow or vaginal bleeding that is heavier than normal
- pink or brown urine, red or black stools
- coughing up blood, or vomiting blood or material that looks like coffee grounds.

How do I take Xarelto®?

- To ensure optimal protection, Xarelto® 15mg and 20mg must be taken with food.

Date of preparation: November 2012
L.GB.10.2012.0954

PATIENT ALERT CARD

Xarelto® 15mg
Xarelto® 20mg

- **Keep this card with you at all times**
- **Present this card to every physician or dentist prior to treatment**

I am under anticoagulation treatment with Xarelto® (rivaroxaban)

Name: _____

Address: _____

Birth date: _____

Blood type: _____

Weight: _____

Other medications/conditions: _____

In case of emergency, please notify:

Doctor's name: _____

Doctor's phone: _____

Doctor's stamp: _____

Please also notify:

Name: _____

Phone: _____

Relationship: _____

Information for health care providers:

- INR values should not be used as they are not a dependable measure of the anticoagulant activity of Xarelto®.

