You have now reached the end of the first questionnaire. Please place your completed questionnaire back into the envelope and seal the envelope. Then, follow the instructions for completion of the second part of the survey.

**Xarelto Risk Minimization Study
Patient Questionnaire #2**

This is the second of two questionnaires. Before you proceed, please make sure you have completed the first questionnaire (found in a separate envelope).

[Patient alert card is included in envelope 2]

The purpose of the second questionnaire is to learn more about your understanding of important safety information related to Xarelto after reviewing the Xarelto Patient Alert Card.

Before you complete this questionnaire, please read through the attached Xarelto Patient Alert Card as if you just had received it for the first time from your doctor.

After you have read the Xarelto Patient Alert Card, please answer the following questions related to the safety information provided in the card.

Q1. Xarelto is a prescription medicine used to thin the blood to prevent blood clots?

- Yes, this is true
- No, this is not true
- I don't know

Q2. Blood thinning medications, such as Xarelto, may cause bleeding. Please remember that this question is asking about your knowledge in general and not about your own experience.

- Yes, this is true
- No, this is not true
- I don't know

Q3. Which of the following are possible signs or symptoms of bleeding while taking Xarelto? Please remember that this question is asking about your knowledge in general and not about your own experience.

Check the box Yes, No, or I don't know for each of the following items.

| | Yes, this may be a sign or symptom of bleeding when taking Xarelto | No, this is not a sign or symptom of bleeding when taking Xarelto | I don't know if this is a sign or symptom of bleeding when taking Xarelto |
|-------------------------------------|---|--|--|
| Pain |  |  |  |
| Swelling or discomfort |  |  |  |
| Headache, dizziness, or weakness |  |  |  |
| Unusual bruising |  |  |  |

Q4. I must not stop taking Xarelto at any time without consulting with my doctor.

- Yes, this is true
- No, this is not true

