- I don't know

Q5. I need to speak to my doctor prior to any intake of other medication(s).

- Yes, this is true
- No, this is not true
- I don't know

Q6. I need to inform my doctor or dentist about Xarelto intake prior to any kind of surgery or invasive procedure.

- Yes, this is true
- No, this is not true
- I don't know

Q7. I need to tell my doctor right away if I have any signs or symptoms of bleeding while taking Xarelto.

- Yes, this is true
- No, this is not true
- I don't know

Q8. Should Xarelto (15 mg and 20 mg tablets) be taken with food?

- Yes
- No
- I don't know

Q9. What should you do to ensure Xarelto is effective in preventing blood clots?

Select all that apply.

- Take Xarelto exactly as prescribed by your Health Care Professional
- Take Xarelto only when you do not feel well
- Do not miss a dose of Xarelto
- I don't know

The next section is about the Xarelto Patient Alert Card that you reviewed before completing the second questionnaire. The Xarelto Patient Alert Card contains important safety information about Xarelto.

Q10. Prior to today, had you received or been given the Patient Alert Card for Xarelto?

- Yes → **Go to Q11**
- No → **Go to Q15**
- I don't remember → **Go to Q15**

Answer questions Q11 – Q14 only if you received a Patient Alert Card for Xarelto.

Q11. Prior to today, had you ever read the Patient Alert Card for Xarelto?

- Yes → **Go to Q13**
- No → **Go to Q12**
- I don't remember → **Go to Q13**

Q12. Is there a reason why you have not read the Patient Alert Card for Xarelto, prior to today?

Select all that apply.

- I haven't taken the medication yet
- Someone else explained it to me
- I lost the patient alert card
- I already knew the information
- I have not had the time yet
- I am not interested in reading it
- Other

Q13. How much of the time do you keep the Xarelto Patient Alert Card with you?

Select the one answer that best applies to you

- All the time
- Some of the time
- None of the time
- I don't know

Q14. Who do you show the Patient Alert Card to?

Select the one answer that best applies to you

- Every doctor or dentist that I visit
- No one, it is just for my information
- Only to healthcare professionals who ask for it
- I don't know

Q15. Prior to today, had someone explained the information in the Patient Alert Card for Xarelto to you?

Select all that apply.

- Yes, a doctor
- Yes, a nurse
- Yes, a pharmacist or someone at the chemists
- Yes, a friend, family member, or carer
- No

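### Section 3.2.5 promises a measure of whether patients know to carry the alert card, but Questionnaire #1 has no such item and none is visible in Questionnaire #2; the one carrying item asks about behaviour, after card exposure

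*Protocol*

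**What the plan says.** Section 3.2.5 of the protocol introduces its list with "The questionnaire will assess patient knowledge of the following concepts". The first entry is receipt and use of the card. The second is knowledge of the card's key safety messages, with five sub-entries, one of which is "Necessity of carrying the patient alert card at all times". The same section states: "The final version of the questionnaire can be found in Appendix D".

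Section 2 sets the behavioural aim alongside the knowledge aim: the study is also to "determine if the patients use and carry the patient alert card with them".

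In Appendix D the only item on carrying is Q13 of Questionnaire #2: "How much of the time do you keep the Xarelto Patient Alert Card with you". The instruction before that group of items is "Answer questions Q11 – Q14 only if you received a Patient Alert Card for Xarelto". At the start of the same questionnaire the patient is told: "please read through the attached Xarelto Patient Alert Card". The card, reproduced in Appendix B, carries the line "Keep this card with you at all times".

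**The concern.** The protocol treats knowing the message and carrying the card as separate targets. Receipt and use has its own entry in Section 3.2.5, and carrying has its own clause in Section 2. The instrument covers the behaviour but not the knowledge.

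The primary objective is awareness and understanding of the key messages, and Section 1 also names carrying the card as one of them. If the form is used as printed, the report can say nothing about how many patients know this message. No analysis can recover an answer to a question that was not asked. Section 1 plans assessments at 18 months, 3 years and 7 years, so an unchanged form would repeat the gap each time.

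The behaviour item has its own weakness. Respondents have just been reminded of the recommended answer, and the question does not tell them to report what they did before that reminder.

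**Working it through.** No sample-size or interval calculation bears on this point. Table 2 of Section 3.2.4 gives the precision of an item that is asked; for this message there is no knowledge item to which any row could apply. The check is a comparison of Section 3.2.5 with Appendix D.

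**Step 1. Knowledge items for each listed message.** All items were read: S1–S2 and Q1–Q19 of Questionnaire #1, and Q1–Q15 of Questionnaire #2.

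| Message in Section 3.2.5 | Questionnaire #1 (before the card) | Questionnaire #2 (after the card) |
|---|---|---|
| Signs of bleeding, when to seek help | Q9, Q13 | Q3, Q7 |
| Treatment compliance | Q10, Q15 | Q4, Q9 |
| Tablets with food | Q14 | Q8 |
| Telling professionals before surgery or a procedure | Q12 | Q6 |
| Carrying the card at all times | none | none visible |

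Four of the five messages have at least one knowledge item in each questionnaire. Carrying has 0 in Questionnaire #1 and 0 in the visible part of Questionnaire #2. The copy reviewed ends at Q15 of Questionnaire #2, with later text removed. Anything there would follow card exposure, so it could not supply an unprompted answer.

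**Step 2. Can Q13 of Questionnaire #2 stand in?**

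- *Content.* Its answers are all, some or none of the time, or don't know. A patient can know the message and still leave the card at home.
- *Respondents.* Those answering no or don't remember at Q10 skip to Q15. Patients without a remembered card therefore contribute nothing.
- *Timing.* It is in Questionnaire #2, after the enclosed card has been read. Section 3.2.6 wants the first questionnaire answered without the card, and no carrying item is asked under that condition.

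Q13 therefore gives a behaviour figure for recipients. It does not give a knowledge figure for patients.

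**Step 3. Time reference of the card items in Questionnaire #2.**

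| Item | Topic | Restricted to before the study day? |
|---|---|---|
| Q10 | Received the card | Yes |
| Q11 | Read the card | Yes |
| Q12 | Reason for not reading it | Yes |
| Q13 | How often it is kept at hand | No |
| Q14 | To whom it is shown | No |
| Q15 | Whether someone explained it | Yes |

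Four of the six items exclude same-day exposure by their wording. The two that ask about recommended behaviour do not.

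**The case against.** **The list may be only a list of topics.** Its lead-in uses the word knowledge loosely, since it also covers receipt and use. On that reading Q13 serves the aim in Section 2, and Section 5 likewise speaks of whether patients carry the card. Part of this stands: Q13 does address the behavioural aim, and the protocol nowhere says that Q13 will substitute for knowledge. But the carrying message sits in the sub-list headed as knowledge of key safety messages, apart from the receipt-and-use entry, so the mismatch remains.

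**The recipient filter.** A reader might infer that asking only recipients inflates the carrying figure. The documents do not support that. A patient without a card cannot carry it, and Q10 is put to everyone, so a figure over all patients can be derived from the data as collected. The choice of denominator belongs to the analysis plan.

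**The before/after pair.** A reader might also take the missing pair as a broken commitment. It is not. Sections 3.2.6 and 3.3 promise re-administration of selected questions only.

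**Prompting.** Q13 does not come immediately after the card: Q1–Q9 and the receipt items precede it, and respondents say they already had the card. Over-reporting is the plausible direction, but nothing in the documents gives its size.

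**Moving Q13 and Q14 into Questionnaire #1.** This is tempting but would do harm. Placed behind a new carrying item they would again be prompted, and the receipt filter would be answered without the card in view for recognition.

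**A new true/false item is easy to guess.** The existing items in that format (Questionnaire #1 Q4, Q8 and Q10–Q13) all state something true. That limitation stands, and the new item would share it with its neighbours.

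**Conclusion.** The point holds as a mismatch between Section 3.2.5 and Appendix D. One of the five listed messages has no knowledge item in Questionnaire #1 and none visible in Questionnaire #2; the other four have items in both. The single carrying item measures self-reported behaviour among recipients after card exposure, without the time restriction used in Q10, Q11, Q12 and Q15. It cannot yield a knowledge estimate, and it is open to over-reporting of unknown size.

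The conclusion rests on two readings: that Appendix D is the form to be used, as Section 3.2.5 says, and that the sub-list means knowledge in the ordinary sense. Country-specific modifications are anticipated, but none described in the protocol fills the gap. Only for Questionnaire #2 does the missing end of the copy leave any doubt. The severity is minor: the other four messages and the study's precision are unaffected.

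**What to change.** 1. Add one item to Questionnaire #1 saying that the card needs to be kept with the patient at all times, with the existing answers (true, not true, don't know). Repeat it in Questionnaire #2 with the other repeated knowledge items.
2. Reword Q13 and Q14 of Questionnaire #2 to ask about the time before the study day, in line with Q10, Q11, Q12 and Q15. Leave both items and their receipt filter where they are. This reduces prompting but does not remove it, so the report should still say that these answers were given after the card had been read.
3. If the form is locked, remove the carrying message from the knowledge list in Section 3.2.5. Report carrying as self-reported behaviour among recipients, asked after card exposure.

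The cost of steps 1 and 2 is a few seconds per patient, translation, and one item that did not go through the cognitive pretesting with 25 patients described in Section 3.3. Step 3 costs one deleted line and a sentence in the report, but leaves the message without a knowledge estimate.
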